Nutritional Intervention-Clinical Trial Protocol

Title: Postprandial Inflammatory and Metabolic Responses Induced by the Authentic Ladotyri Mytilinis PDO Cheese and Italian Parmesan PDO Cheese

NCT IDENTIFIER: NCT05788887

16 December 2022

1. Protocol Summary

This is the protocol of a randomized, blinded and controlled nutritional intervention – clinical study to investigate the postprandial effect of consuming Authentic Ladotyri Mytilinis, PDO cheese on the lipid, glycemic profile and the oxidative status of the blood of healthy volunteers.

The acute nutritional intervention – clinical study is a cross over design (acute study), with two axes. The purpose of this study was the investigation of the postprandial metabolic responses, after the intake of a traditional, Ladotyri Mytilinis cheese, compared to corresponding responses after an Italian Parmesan cheese consumption, in healthy participants.

The study volunteers will be healthy, aged 18-65 years, residing during the intervention in Lemnos. The study will take place in the specially designed space of the Human Nutrition Unit, University of the Aegean and in voluntary collaboration with the General Hospital of Limnos. The duration of the study will be 7 days.

Participants will be randomly divided into two groups. During the first day, the first group will consume Italian Parmesan, PDO cheese (control group) and the second group will consume Authentic Ladotyri Mytilinis, PDO cheese (intervention group), together with two slices of bread, while 1 glass of water will be available for each volunteer [1st test period]. After a 7-day washout period, the same volunteers will come to the specially designed area and the process will be repeated, with the difference that the control group of the 1st day will belong to the intervention group, and the intervention group will belong to the control [2nd test period].

In each test period, blood samples will be taken from all consecutive volunteers in a fasted state, as well as 30 minutes, 1.5 and 3 hours after consuming meals. This will be followed by analysis of the samples and statistical processing of the results of the analyzes to present data regarding the acute effect of meal consumption on the postprandial biomarkers of lipemia, glycemia and oxidative stress in healthy volunteers.

2. Theoretical background and study objectives

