2.2. Study Objectives / Research Questions

Purpose

The purpose of this study was the investigation of the postprandial responses on serum total, HDL-, LDL- cholesterol, triglycerides, uric acid, glucose and plasma Total Antioxidant Capacity (TAC), after the intake of a traditional, Authentic Ladotyri Mytilinis cheese, compared to corresponding responses after an Italian Parmesan cheese consumption, in healthy participants.

Research Questions

The research questions of this clinical study are the following:

- ✓ Which is the acute effect of ALM-PDO cheese consumption, in the framework of a high-fat and carbohydrates meal, on the postprandial biomarkers of lipemia, glycemia and oxidative stress?
- ✓ Does the postprandial inflammatory and metabolic responses to ALM-PDO cheese differs, compared to Italian Parmesan PDO cheese? LDL- cholesterol and triglycerides determined at 3h after the meal intake, was set as the primary endpoint of the present, pilot study.

3. Summary presentation / study design

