3.1. Overview

A nutritional intervention – clinical study of self-comparison design (cross over design: acute study) will take place in a sample of healthy volunteers, where the difference in the effectiveness of the nutritional intervention will be evaluated in the same volunteer. This means that the response of lipemia, glycemia and oxidative stress biomarkers to the intervention meal will be compared with their response to the control meal, in the same volunteer each time. The specific research will be carried out in the specially designed area of

the Human Nutrition unit of the University of the Aegean and in collaboration with the hospital of Lemnos, with which a collaboration protocol has been concluded with the University of the Aegean.

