3.2. Study design

In a total sample of approximately 10 healthy volunteers, the number of which was determined through a special statistical program for calculating the required sample of the research to draw safe and reliable conclusions, a nutritional intervention – clinical study of cross-over design will be carried out. The study for each participant will be 7 days long, including the washout period.

Each participant during the first test period and in a state of 12-hour fasting, will be asked to come in the morning hours of 9 am. - 12:30 p.m., the specially designed blood collection room of the Human Nutrition Unit, Department of Food Science and Nutrition, University of the Aegean. In this specially designed area, a blood sample (baseline) will be taken by a doctor or competent staff of the Lemnos Hospital. This will be followed by a discussion with the healthy volunteer, signing of a declaration of participation, filling in a questionnaire and a 24-hour recall of food consumption. The questionnaire that each volunteer will fill out on the first day of the start of the study concerns their medical history and general information about their habits (especially dietary). Afterwards, a meal will be served that will include 2 slices of bread (80g- 40g each) and 2 pieces of cheese (100g- 50g each piece), according to the group each volunteer belongs to, accompanied in each case by 1 glass of water. The consumption of each meal will be completed within the time period of 15 minutes by all participants (controlled). Finally, the following blood samplings will be carried out for the volunteers, which will be conducted 30 minutes, 1.5 and 3 hours after the completion of the meal.

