4.1. Sample size calculation

In order to note a 40% difference in the postprandial response of triglycerides and/or LDL-cholesterol and in order to have an 80% chance of a statistically significant difference between the studied groups at a significance level of 5%, a necessary sample of 10 subjects was calculated.

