6.3. Statistical analysis

After the above analyzes have been carried out using a special biochemical analyzer, the use of the statistical package SPSS (Statistical package for social sciences: SPSS) will follow in order to record, process and analyze the results of the study. The Kolmogorov–Smirnov test was applied to check normality. The main participants' characteristics will be analyzed by descriptive statistics. Differences in baseline values between groups for each biomarker tested, will be analyzed using a paired sample two tailed t test. Repeated ANOVA measures with Geisser–Greenhouse correction will be conducted, for serum total, HDL-, LDL- cholesterol, triglycerides, glucose, uric acid and plasma Total Antioxidant Capacity (TAC). If time or group was significant, multiple comparison post hoc Bonferroni test will be performed for the comparison of concentrations. To check changes in the metabolic biomarkers from baseline to postprandial responses (within-group variation), the Wilcoxon sign-rank test will be carried out.

7. Maintenance of study records

The study files will remain securely registered for a maximum of 3 years from the date of their registration in special areas of the Human Nutrition Unit, University of the Aegean. Study records should be kept for a maximum of 2 years after the last marketing approval, or longer if required by local regulations.

8. Ethics, Consent and Privacy Statement

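### The primary endpoint, the Ladotyri-versus-Parmesan comparison at 3 h, has no test of its own in section 6.3, and its significance level is left open

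*Combined protocol and SAP*

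**What the plan says.** Section 2.2 asks whether responses to the two cheeses differ and states: "LDL- cholesterol and triglycerides determined at 3h after the meal intake, was set as the primary endpoint of the present, pilot study". That is two markers at one time point.

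Section 4.1 sizes the study for "a 40% difference in the postprandial response of triglycerides and/or LDL-cholesterol" with 80% power, and ends: "at a significance level of 5%, a necessary sample of 10 subjects was calculated". It gives no SD, no named test and no division of the 5% between the markers.

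The design is a crossover. Section 3.1 says that each response "will be compared with their response to the control meal, in the same volunteer each time". Section 1 says that in the second period "the control group of the 1st day will belong to the intervention group, and the intervention group will belong to the control". Blood is taken fasting and at 30, 90 and 180 minutes.

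For the analysis, section 6.3 says "Repeated ANOVA measures with Geisser–Greenhouse correction will be conducted", for seven biomarkers alike, and then "If time or group was significant, multiple comparison post hoc Bonferroni test will be performed for the comparison of concentrations". A paired t test is named for baseline values, and a Wilcoxon signed-rank test for change from baseline within each group.

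**The concern.** A primary endpoint needs one test whose contrast and level are fixed in advance. Here neither is. The 3 h comparison of the cheeses is not named anywhere in section 6.3. It can be reached only as one of an unlisted set of post hoc comparisons, and only if a main effect of time or of group is significant.

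The condition also fits the question poorly. A time effect can arise when both cheeses behave identically, so it can open the step without any cheese difference. Cheese-by-time, the term that captures a different postprandial course, is not part of the rule.

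Section 2.2 joins the two markers with *and*, section 4.1 with *and/or*, and section 6.3 is silent. Whoever analyses the data could test each 3 h contrast at 0.05, 0.025, 0.0167 or 0.0125, or count one marker or both, and each choice would fit the text.

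**Working it through.** **1. Which named procedure tests the primary endpoint?**
- Paired t test: baseline values only.
- Wilcoxon test: change within a cheese, so it does not compare cheeses.
- Repeated-measures ANOVA: all seven markers and several times, with no marker, time or contrast singled out.
- Bonferroni step: could contain the 3 h cheese contrast, but its members are not listed.

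No other section supplies the missing test.

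**2. The plan's figure of 10.** It cannot be reproduced, because no SD or test is given. It can be back-solved. For a two-sided paired t test, power = P(T > t(1−α/2, n−1)), with T noncentral t on n−1 degrees of freedom and noncentrality d√n. With n = 10, α = 0.05 and power 80%, d = 0.996. Reading the 40% as 40 percentage points, the SD of the paired difference would be 40/0.996 ≈ 40.2 points. Assumed SDs of 30, 40, 50 and 60 points would need 7, 10, 15 and 20 subjects. The power figures below all assume d = 0.996.

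**3. Power when the level is divided.** Same formula, n = 10, d = 0.996, level 0.05/k:

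| k | Example of the family | Level | Power |
|---|---|---|---|
| 1 | 3 h contrast, one marker | 0.05 | 80% |
| 2 | 3 h contrast, both markers | 0.025 | 68% |
| 3 | three postprandial times, one marker | 0.0167 | 60% |
| 4 | all four times, one marker | 0.0125 | 54% |

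**4. False-positive chance if either marker counts at 0.05.** For independent markers it is 1 − 0.95² = 9.75%. In simulated pairs of paired t tests at n = 10 it is about 9% at marker correlation 0.5 and about 7.5% at 0.9. These rates do not depend on the assumed d.

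**5. If both markers must succeed at 0.05.** No division of the level is needed, but joint power is at most 80%, and 0.80 × 0.80 = 64% if the markers are independent.

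**6. The condition.** I simulated a cheese difference at 3 h only (d = 0.996), with equal SDs and a common correlation of 0 to 0.9 among the cheese differences at the sampling times. The *group* term is significant in about 29% of trials at correlation 0, falling to about 11% at 0.9, if all four samples enter the ANOVA. If only the three postprandial samples enter, it falls from about 37% to 16%. Section 6.3 does not say whether the fasting sample is included. These figures describe the *group* term alone; *time* may open the step anyway.

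**The case against.** **It is a pilot, and a repeated-measures ANOVA with Bonferroni follow-up is ordinary practice.** Section 2.2 does use the word pilot. But section 4.1 justifies the sample size by the chance of a significant result on these two markers, and a study justified that way should say which test that is. The label limits the severity; it does not supply the test.

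***And/or* in section 4.1 is sample-size wording, not a success rule.** This stands. A reader might infer that the trial's false-positive rate is 9.75%. The documents do not say so: that rate applies only if either marker at 0.05 would be counted as success.

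**The condition may do no harm.** This also stands. A reader might infer that it would block a true 3 h difference. Section 2.1 cites a significant triglyceride rise 2 hours after a cheese meal, so a time effect would probably open the step for triglycerides. For LDL cholesterol the documents do not show either way. The low figures for *group* therefore do not establish a loss.

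**Period.** Section 6.3 has no period term, and a reader might infer that the cheese contrast is biased. With equal sequences it is not. Bias needs both unequal sequences and a period effect, and the documents give neither; the planned size is given only as "In a total sample of approximately 10 healthy volunteers".

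**Conclusion.** The point holds as a gap in specification that should be fixed. The two primary markers have no designated 3 h test, no listed Bonferroni family and no two-marker rule, so the level of the headline result is undefined. That much follows from sections 2.2, 4.1 and 6.3 without any numerical assumption.

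The possible size is a false-positive chance of up to 9.75% against 5% if either marker may count (independent markers), or, in the other direction, power of 68%, 60% or 54% in place of 80% as the level is divided by two, three or four. The power figures rest on the back-solved d = 0.996 and a two-sided paired t test, neither of which the documents state.

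The documents do not show that the condition costs power, that the cheese contrast is biased by period, or that 10 subjects are too few.

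**What to change.** In section 6.3:
- For each of LDL cholesterol and triglycerides, prespecify one unconditional within-participant Ladotyri-minus-Parmesan comparison at 3 h with a 95% CI, adjusted for the difference between the two fasting values. Enter that covariate uncentred, so that the intercept is the cheese difference at equal fasting values. The estimate and test are then the same for the 3 h value and for the change from fasting. A plain paired comparison of one declared endpoint (3 h value or change) would also close the gap.
- State the two-marker rule: for example 0.025 each, or both required at 0.05.
- Keep the ANOVA as supportive, report cheese-by-time, and list the comparisons that share the Bonferroni correction.
- As a secondary refinement, add period (sequence coded +1/−1 in the model for the paired difference). At 5/5 sequences this costs about 2 to 3 points of power for r up to 0.5 (r is defined below). It protects against bias only if the sequences end unequal and a period effect exists.

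In section 4.1, restate the power for the chosen test and rule, with the SD and the scale of the 40%.

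**Cost.** Wording only; no visits, samples or extra enrolment. The stated power may change, in a direction the documents cannot settle, because they do not say whether the 40% refers to the 3 h value or to the change from fasting. The table gives simulated power for the adjusted test with period (n = 10, 5/5, 7 degrees of freedom, equal SDs). Here r is the correlation between the fasting and 3 h cheese differences. With d = 0.996 on the change, the 3 h difference in SD units is 0.996 × √(2(1−r)), so the two readings meet at r = 0.5.

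| r | d on 3 h difference: 0.05 / 0.025 | d on change: 0.05 / 0.025 |
|---|---|---|
| 0 | 72% / 57% | 94% / 87% |
| 0.3 | 75% / 62% | about 88% / 77% |
| 0.5 | 83% / 71% | 83% / 70% |
| 0.7 | 93% / 86% | 78% / 65% |
| 0.9 | 99.9% / 99.7% | 74% / 60% |

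The small differences at r = 0.5 are simulation error.

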After a seven-day washout period, on the eighth day (2nd test period) the same participants will be asked to come again, in a fasting state, to the specially designed area of the University of the Aegean, at the predetermined morning hours to repeat the procedure nutritional intervention and blood sampling. In other words, a blood sample will be taken by a doctor or competent staff of the Limnos Hospital, followed by a discussion with the volunteer and completion of a 24-hour recall of food consumption questionnaire. The questionnaire that the participants will complete at the start of the second test period is to record their specific eating habits during the washout period (ie the interval between the two periods of the intervention). The meals served to the volunteers are determined by the control or intervention group to which they belong. After each meal is consumed within the 15-min timeperiod, subsequent blood sampling will be done for participants 30, 90, and 180 minutes (min)after the completion of the meal .

4. Enrollment of participants and case of study withdrawal

The goal is to gather an initial sample of people from the Greek area in order to achieve the collection of a required number of cases for study. The research team will then review the inclusion/exclusion criteria and select the participants who will receive the meals in the two test periods of the study.

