4.5. Participant withdrawal criteria

Participants are free to withdraw from the study at any time. Accordingly the researcher will be able to ask the participant to leave the study if:

- o Clinical adverse events, laboratory abnormality, or other medical condition or condition are identified that endanger the participant from remaining in the study
- o Participants meet one of the aforementioned exclusion criteria (either newly developed or not previously identified) that precludes further participation in the study
- o Participants appear to not adequately adhere to protocol requirements

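### Section 6.3 names no period or sequence term for a randomised two-period crossover, and nothing says the two sequences will be equal in size

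*Combined protocol and SAP*

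**What the plan says.** The Protocol Summary (section 1) sets out a two-treatment, two-period crossover with random order: "Participants will be randomly divided into two groups". One group eats Parmesan and the other Ladotyri on day 1. The procedure is then repeated "with the difference that the control group of the 1st day will belong to the intervention group", and the other group switches the opposite way. Section 3.2 fixes the interval: "After a seven-day washout period, on the eighth day (2nd test period) the same participants will be asked to come again". It also provides for a questionnaire at the second visit "to record their specific eating habits during the washout period".

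Section 2.2 makes LDL-cholesterol and triglycerides at 3 h the primary endpoint. On sample size, section 4.1 states that "a necessary sample of 10 subjects was calculated", while section 3.2 is looser: "In a total sample of approximately 10 healthy volunteers". Section 4.5 adds: "Participants are free to withdraw from the study at any time".

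Section 6.3 is the whole analysis plan. The between-cheese analysis is a repeated-measures ANOVA with Geisser–Greenhouse correction. The model terms are not listed. The only factors named appear in the post hoc rule: "If time or group was significant, multiple comparison post hoc Bonferroni test will be performed for the comparison of concentrations". Period and sequence appear nowhere in 6.3. No section gives a sequence ratio, block size or statement of equal numbers.

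**The concern.** Each participant's Ladotyri-minus-Parmesan difference is also a difference between two visits a week apart. Anything that moves all participants between those visits (familiarity with the procedure, season, assay run) enters that difference with a plus sign in one sequence and a minus sign in the other. Randomising the order makes it possible to separate this shift from the cheese effect, but only if the analysis uses the order.

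If it does not, two things can happen. With equal sequences the shift cancels from the mean but stays in the spread, so the test becomes conservative and loses power. With unequal sequences part of the shift also stays in the estimate. Equal sequences are not assured: no ratio is given, the total is approximate, and withdrawals are allowed. With about 10 people and power planned at 80%, there is little room for avoidable error variance.

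The washout is aimed at carry-over from the first meal. It does not deal with a difference between visits that is common to everyone.

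**Working it through.** **Inputs.** From section 4.1: N = 10, power 80%, significance level 5% (two-sided assumed), difference 40%. From sections 1 and 3.2: two sequences, two periods, ratio not stated. Not in the documents, so assumed: the SD, the size of any day 1 to day 8 shift, and the allocation method. A paired t test on the 3 h values stands in for the group contrast of the ANOVA.

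**1. The plan's own figure.** Section 4.1 gives no SD, so N = 10 cannot be reproduced from its inputs; the SD has to be solved for. For a paired t test with n = 10 and 9 df, the noncentral t gives 80% power at a standardised difference of 0.996. The SD of the within-person difference is then 40/0.996 = 40.2 points. (The normal approximation gives (1.960 + 0.842)/√10 = 0.886, an SD of about 45.) I use 40.2. The standard error is 40.2/√10 = 12.7.

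**2. What a shift does.** Let τ be the cheese effect (Ladotyri minus Parmesan), π the period 1 minus period 2 shift, n1 the number with Ladotyri first and n2 the number with Parmesan first. A participant's cheese difference has expectation τ + π in the first sequence and τ − π in the second. Therefore:

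- Mean difference = τ + π(n1 − n2)/n.
- Expected sample variance = σ² + π²[1 − ((n1 − n2)/n)²] × n/(n − 1).

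At 5:5 the bias is zero. The apparent SD rises from 40.2 to √(40.16² + 100 × 10/9) = 41.5 for a 10-point shift, and to √(40.16² + 400 × 10/9) = 45.4 for a 20-point shift.

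Bias in either direction, for shifts of 10 and 20 points:

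- 5:4 (one dropout from 5:5): 10/9 = 1.1 and 20/9 = 2.2, against a standard error of about 13.4.
- 6:4: 10 × 0.2 = 2 and 20 × 0.2 = 4.

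**3. Power with a period term.** The standard error is (σ/2)√(1/n1 + 1/n2), on n − 2 df. At 5:5 it is 20.1 × √0.400 = 12.7, with power 78.7%. At 6:4 it is 20.1 × √0.417 = 13.0, with power 77.1%. Neither depends on the size of the shift.

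**4. Power without the term** (400,000 simulations per cell, true effect 40 points):

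| Split | Assumed shift | Without term | With term |
|---|---|---|---|
| 5:5 | 0 | 80% | 79% |
| 5:5 | 10 | 78% | 79% |
| 5:5 | 20 | 72% | 79% |
| 6:4, bias opposes effect | 0 | 80% | 77% |
| 6:4, bias opposes effect | 10 | 74% | 77% |
| 6:4, bias opposes effect | 20 | 62% | 77% |

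When the bias favours the effect at 6:4, power is 82% and 80%, but from an inflated estimate.

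**5. Type I error without the term**, for shifts of 10 and 20 points: 4.4% and 3.0% at 5:5; 4.6% and 3.7% at 6:4; 5.4% and 6.1% at 7:3.

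**6. How likely is imbalance?** If 10 people were allocated by simple randomisation (an assumption), 5:5 has probability 252/1024 = 25%, 6:4 has 420/1024 = 41%, and 7:3 or worse has 352/1024 = 34%.

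**7. Check of the proposed regression.** Take d as period 1 minus period 2, with effect 40, shift 20 and no noise. Ladotyri first gives d = 40 + 20 = 60; Parmesan first gives d = −40 + 20 = −20. Coding sequence +1/−1, the slope is (60 − (−20))/2 = 40 and the intercept is (60 + (−20))/2 = 20. The slope recovers the cheese effect and the intercept the shift.

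**The case against.** **No shift is shown.** This is true. The protocol also standardises the two visits: fasting, morning hours, the same bread, cheese weight and water, a 15-minute eating limit, the same sampling times and supervised eating. These features narrow the room for a period effect without excluding it. The recorded but uncontrolled washout diet is not evidence of one either: it would vary between people in no stated direction, and a period term does not remove that kind of noise.

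**The term can cost more than it saves.** With no shift it does, as the table shows. At 5:5 a 10-point shift makes only about one point of difference. A clear gain at 5:5 needs a shift near 20 points, half the planned effect.

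**A shift may cancel.** Section 4.1 is powered on the postprandial response. If that means change from fasting, a shift that moves fasting and 3 h values equally drops out. This does not remove the point, because section 2.2 defines the primary endpoint by the 3 h determinations.

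**Time or group might already cover period or sequence.** This is unlikely. Time beside group in an ANOVA of serial blood samples most naturally means the sampling times. Section 6.3 compares baseline values between groups with a paired test, so group there means cheese.

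**Stronger readings that a reader might infer.** One is that period will be left out, or that the sequences will be unequal. The text is silent on both, and 5:5 may be intended. Another is a serious false-positive problem. Up to 7:3, type I error stays at about 6% or below for the shifts in the table. It reaches 10.5% at 8:2 with a 20-point shift, a split that blocking would prevent. A third is a collapse in power: a 40-point shift would bring 5:5 power down to 48%, but such a shift equals the whole target effect and nothing in the documents suggests it.

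**Conclusion.** The gap is real: a randomised two-period crossover has an analysis section that names neither period nor sequence, and a protocol that does not say the sequences will be balanced. It is a gap in specification with a cheap improvement available. It is not a demonstrated error or a demonstrated bias.

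The size is modest and conditional. Under a back-solved SD of about 40 points and assumed shifts of 10 to 20 points, omitting period costs about 1 to 7 points of power at 5:5. At 6:4, with the bias opposing the effect, it costs about 3 to 15 points and moves the estimate by 2 to 4 points. One dropout from 5:5 produces a bias that is small against the standard error. These figures rest on a paired t stand-in, an SD that the documents do not give, and a shift that may be zero. The case for acting is that the data will already exist, the cost at 5:5 is about one point of power, and naming the model in advance prevents a choice made after the results are seen.

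**What to change.** 1. State in the protocol that the two sequences will be allocated in balanced blocks with equal numbers: 5:5 if N is fixed at 10.
2. In section 6.3, for each 3 h primary outcome, report the period-adjusted cheese effect. Regress each participant's period 1 minus period 2 difference on sequence, coded +1 for Ladotyri first and −1 for Parmesan first. Equivalently, include period in the model.
3. Keep the planned repeated-measures ANOVA for the time course, and list its terms.

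The cost is wording plus a blocked allocation list. No new data are needed and the regression runs in SPSS. The period term uses one error degree of freedom. With no shift, power goes from 80% to about 79% at 5:5 and 77% at 6:4, which is why balanced allocation should go with it.

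### Section 6.3 triggers its follow-up tests on the time or group main effect and does not name meal-by-time, the effect that tests whether the response differs between the cheeses

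*Combined protocol and SAP*

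**What the plan says.** Section 2.2 poses the comparative question: "Does the postprandial inflammatory and metabolic responses to ALM-PDO cheese differs, compared to Italian Parmesan PDO cheese". Section 3.1 describes the comparison as one of responses within the same volunteer: "the response of lipemia, glycemia and oxidative stress biomarkers to the intervention meal will be compared with their response to the control meal". Section 2.2 also fixes the primary endpoint: "LDL- cholesterol and triglycerides determined at 3h after the meal intake, was set as the primary endpoint". Section 1 gives the sampling: a fasting sample, "as well as 30 minutes, 1.5 and 3 hours after consuming meals". That makes four samples per meal.

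Section 6.3 lists four inferential steps:

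- Baseline: "Differences in baseline values between groups for each biomarker tested, will be analyzed using a paired sample two tailed t test".
- Main model, for seven biomarkers: "Repeated ANOVA measures with Geisser–Greenhouse correction will be conducted". Its factors and terms are not listed.
- Follow-up: "If time or group was significant, multiple comparison post hoc Bonferroni test will be performed for the comparison of concentrations".
- Change from baseline, labelled within-group: "To check changes in the metabolic biomarkers from baseline to postprandial responses (within-group variation), the Wilcoxon sign-rank test will be carried out".

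Meal-by-time is not named anywhere in the protocol. Nor is a between-cheese comparison of change from fasting, or a dedicated between-cheese test at 3 h.

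**The concern.** A difference between cheeses in response from fasting is, in a repeated-measures ANOVA, the meal-by-time interaction. The two effects that section 6.3 acts on ask other questions. *Time* asks whether values move after eating, whichever cheese was eaten. *Group* (read here as the meal, as the crossover description uses the word) asks whether the average level over all four samples differs, and one of those samples is drawn before any cheese is eaten.

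Two errors of interpretation become possible. A late difference can be reported as absent because *group* is not significant. A *time* effect, or a difference in level already present at fasting, can be reported as a difference in response. With seven biomarkers and the interaction unnamed, the choice of which term to report could also be made after the results are seen.

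**Working it through.** **1. The plan's own figure.** Section 4.1 gives 10 subjects for a 40% difference, 80% power and a 5% level. No SD, correlation or test is given, so the figure cannot be reproduced. It can be inverted. For a two-sided paired t test with n = 10 (9 df), 80% power needs a standardised difference of 0.996. That implies an SD of the within-person difference of 40 / 0.996 ≈ 40 percentage points. I use δ = 0.996 SD as the 3 h difference.

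**2. What *group* measures.** Let d0, d30, d90 and d180 be the mean differences between cheeses at the four samples. *Group* tests (d0 + d30 + d90 + d180) / 4.

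- Difference at 3 h only: (0 + 0 + 0 + δ) / 4 = δ/4.
- Equal difference at all post-meal times: (0 + δ + δ + δ) / 4 = 3δ/4.
- Constant offset already present at fasting: 4δ/4 = δ, although the responses are identical.

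With unit SDs and common correlation ρ between the paired differences, the SD of this average is √((1 + 3ρ)/4). For a 3 h-only difference at ρ = 0.5 the noncentrality is (0.249 / 0.791) × √10 ≈ 1.0. A direct test at 3 h has 0.996 × √10 ≈ 3.15.

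**3. Power of the two effects.** Assumptions not in the documents: normal paired differences, equal SDs at each time, and ρ from 0.3 to 0.8. I simulated 40,000 trials of 10 people per cell. *Group* is a one-sample t test on the average difference. Meal-by-time is a repeated-measures ANOVA on the differences with Geisser–Greenhouse correction. Entries are the percentage significant at 5%, *group* / meal-by-time.

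| Difference at 0, 30, 90, 180 min | ρ = 0.3 | ρ = 0.5 | ρ = 0.7 | ρ = 0.8 |
|---|---|---|---|---|
| 0, 0, 0, δ | 18 / 65 | 15 / 82 | 13 / 97 | 12 / 99.8 |
| 0, δ/6, δ/2, δ | 40 / 52 | 31 / 69 | 26 / 92 | 25 / 99 |
| 0, δ, δ, δ | 86 / 65 | 75 / 82 | 66 / 97 | 63 / 99.9 |
| δ, δ, δ, δ (same response) | 98 / 3 | 94 / 3 | 89 / 3 | 86 / 3 |

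The simulation standard error is at most √(0.25/40,000) = 0.25 percentage points.

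**4. When the *time or group* rule opens.** This depends on the time course averaged over both cheeses. I gave that average half the SD of the difference, which corresponds to equal, independent noise for the two meals.

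- Average flat (the two cheeses' effects cancel exactly): the rule opens in 15–21% of trials for a 3 h-only difference and about 28–42% for the rising one, over ρ = 0.3 to 0.8.
- One cheese leaves the marker flat and the other moves it: it opens in 71–99.8% and 72–99%.

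The rule is therefore a poor filter in either case. Where a marker moves after any meal, it opens through *time* and says nothing about the cheeses.

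**The case against.** The strongest reply is that section 6.3 does not exclude the interaction. The ANOVA terms are unlisted, SPSS prints meal-by-time by default, and the follow-up comparison of concentrations could mean cheese against cheese at each time. This stands in part. A reader might infer that no planned test could compare the cheeses' responses. The text supports only that the relevant effect is not named and the follow-up contrasts are not defined.

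A reader might also infer that the rule usually hides a real late difference. Step 4 shows that this needs a flat average time course. Section 2.1 expects triglycerides to rise after a cheese meal, so for that primary marker the rule would probably open.

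Nor is *group* uninformative. With no fasting difference it picks up a sustained post-meal difference in 63–86% of trials, and it beats meal-by-time at ρ = 0.3.

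Finally, the constant-offset row is not evidence of a raised false-positive rate. It assumes a true mean shift at fasting. Randomised order does not lead one to expect that, and with no true difference *group* keeps its 5% level. The row shows only that *group* does not measure response.

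What remains is that the stated rule acts on two effects, neither of which isolates a difference in response from fasting, and leaves out the one that does.

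**Conclusion.** The point holds as a should-fix. That section 6.3 omits meal-by-time is a matter of text and needs no simulation. The size of the loss depends on the assumed SDs, correlations and shape of the difference, none of which the documents give. It is large for a 3 h-only difference, moderate to large for a rising one, and reversed for an even post-meal difference with weakly correlated samples.

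It is not a must-fix. The primary comparison at 3 h is a single between-cheese contrast that should be specified in its own right. Once that is set aside, the ANOVA rule matters mainly for the five non-primary markers and the time courses, in a study that section 2.2 calls a pilot.

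**What to change.** Replace the follow-up sentence in section 6.3 with a rule to this effect:

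- For each biomarker the model contains meal, time and meal-by-time, all within person, with period accounted for (for example, through the randomised sequence).
- Question 2 is tested by meal-by-time, with the Geisser–Greenhouse correction.
- Bonferroni-adjusted between-cheese comparisons of change from fasting at 30, 90 and 180 min follow from that test.
- The *time* effect is descriptive. The *group* effect, which includes the fasting sample, is not used as the test of response.
- The 3 h between-cheese comparison for LDL-cholesterol and triglycerides is made directly and does not depend on any preceding ANOVA result.

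This costs a few sentences and needs no new data, visits or software. The statistical price is some loss of power for a flat post-meal difference when samples are weakly correlated (65% against 86% at ρ = 0.3). For the non-primary markers, meal-by-time is itself a filter and can miss real differences at low correlation.
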